### **12.3.2 Pharmacokinetics**

- The PK population will be used for evaluation of PK parameters.
- All plasma PK parameter calculations ( $C_{trough}$  values) will be performed using actual time points (actual date and time of each blood draw) calculated relative to the time of study drug administration.
- Graphical comparison of  $C_{trough}$  values (collected  $\geq 12$  hours after the prior dose) on Week 0 (Day 1), Week 4 (Day 28  $\pm 3$  days), and Week 24 (Day 168 [ $\pm 5$  days]) will be used to assess steady state levels.
- All descriptive analyses and generation of tables, listings and figures, will be performed using a validated installation of Phoenix WinNonlin® version 8.0 (Pharsight, Cary, North Carolina, USA) as part of a 21 CFR Part 11 compliant database system (Pharsight Knowledgebase Server “PKS”).
- The final analysis will be conducted after all subjects have completed the study, all PK samples collected, have been analyzed, and the database is locked.
- Subject demographics, baseline characteristics, disposition, dosing dates and dosing times, and compliance data necessary to support analysis of PK, will be imported (SAS datasets) from the clinical safety and efficacy database (eCRF data).
- If additional analyses are required to supplement the planned PK analyses, they may be performed and will be identified in the appropriate section of the CSR. Any substantial deviations from the planned SAP will be updated in the SAP and approved.

### **12.3.3 Handling of PK Concentration Values Below the Limit of Quantification**

The lower limit of quantification of the assay in plasma is 0.0555 ng/mL for both sofpironium and BBI-4010. Concentrations that are reported as below the limit of quantitation will be set to 0 for the calculation of the descriptive statistics for the drug concentration summary.

### **12.3.4 Handling of Missing PK Sampling or Concentration Data**

Missing sampling or concentration values will not be imputed but left missing in the calculation of mean concentrations. Concentrations that are not reportable due to technical artifact or ambiguity will be treated as missing values. If the actual sampling time is missing, but a valid concentration value has been measured, the scheduled protocol time will be used for the calculation of mean concentration.

### **12.3.5 Handling of PK Outliers**

On a case by case basis, it may be necessary to exclude individual bioanalytical data from the calculation of mean concentrations because they are erroneous, abnormal or appear implausible to the pharmacokineticist in charge of the analysis. Any excluded data will be

flagged in the individual data listings. The reason for exclusion will also be documented. If the exclusion has a meaningful impact on the overall interpretation of the results, it will be discussed with the Sponsor.

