3.1.1.2 Pharmacokinetics

To assess the systemic exposure (C_{trough}) of sofspironium and its primary metabolite (BBI-4010) following topical application of ~ 0.67 mL of sofspironium bromide gel, 15% applied topically to each axilla, once daily (QD) for up to 24 weeks.

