### **12.3.7 Handling of Individual PK Data and Summary Data Formats**

The actual values as provided from the bioanalytical laboratory will be displayed as individual concentration-time listings. Drug concentrations will be used to calculate the mean using descriptive analysis. For summary tables, the descriptive statistics will be rounded to one more digit than the individual values for the arithmetic mean, SD, median and geometric mean, and to the same number of digits for the minimum and maximum values. The number of non-missing observations (N) will be reported as an integer number. The coefficient of variation (CV) (%) and geometric CV% will be reported as a percentage (CV\*100) as an integer number.

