## 15.2 Appendix B: Preliminary Table of Contents for Tables, Listings, Figures for PK Tables

Table 14.x.x.1 Summary of Mean (SD), CV%, Median, Min and Max Sofpironium Plasma Concentrations (Ctrough values) by Week

Table 14.x.x.2 Summary of Mean (SD), CV%, Median, Min and Max Metabolite Plasma Concentration (Ctrough values) by Week

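### SAP 12.3.5 lets a reportable trough concentration be left out of the mean because it looks odd to one analyst, with no objective criterion and no summary that keeps the value in

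*SAP*

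**What the plan says.** SAP 12.3.5 states that, case by case, "it may be necessary to exclude individual bioanalytical data from the calculation of mean concentrations" and gives the grounds as "because they are erroneous, abnormal or appear implausible to the pharmacokineticist in charge of the analysis". Two safeguards follow. Excluded data will be "flagged in the individual data listings. The reason for exclusion will also be documented". And: "If the exclusion has a meaningful impact on the overall interpretation of the results, it will be discussed with the Sponsor".

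Neighbouring sections bear on how far this reaches:

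- SAP 12.3.4: "Concentrations that are not reportable due to technical artifact or ambiguity will be treated as missing values".
- SAP 12.3.3: concentrations below the limit of quantification (0.0555 ng/mL for both analytes) are set to 0 for descriptive statistics.
- SAP 12.3.6: summaries use samples taken at least 12 hours after the previous dose and before the next one.
- SAP 12.3.7: "The actual values as provided from the bioanalytical laboratory will be displayed as individual concentration-time listings".
- SAP 13.3.2 plans arithmetic mean, SD, CV, median, minimum and maximum, plus a plot of mean (±SD) by week to judge exposure, accumulation and steady state. Appendix B lists the matching table as "Summary of Mean (SD), CV%, Median, Min and Max Sofpironium Plasma Concentrations".

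Systemic exposure is a primary objective (Protocol 3.1.1.2), and Ctrough at Weeks 4 and 24 is listed among the primary endpoints (Protocol 3.2.1.2, SAP 7.2.1.2). Protocol 11.4.2 has no outlier rule and leaves further PK detail to the SAP.

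**The concern.** Of the three grounds, only error can be tied to a recorded cause. The other two are opinions about the number itself, formed with the number in view. SAP 12.3.5 sets no numerical criterion, asks for no supporting evidence from site or laboratory, names no second reader, fixes no point by which the decision must be made, and plans no summary with and without the value. Discussion with the sponsor depends on someone finding the effect meaningful, and the SAP states neither the threshold nor who decides.

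At stake is the summary of a primary endpoint in at most 24 children and adolescents. Mean Ctrough by week is the planned display for accumulation, and a high Week 24 value is what accumulation would look like. If such a value is dropped because it looks unusual, the main table and figure could understate exposure without any assay or sampling fault having been shown.

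**Working it through.** **No figure in the plan to reproduce.** The 24 subjects are the enrolment cap carried over from Study BBI-4000-CL-105 (Protocol 11.1). The PK analysis is descriptive, and no between-subject CV is given.

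**Step 1: what the rule adds.** Non-reportable assay results are already missing (SAP 12.3.4). The sampling window is already applied (SAP 12.3.6). Dosing errors and out-of-window samples are protocol violations, for which the sponsor decides on censoring (Protocol 9); SAP 12.8 also says that violations often make data non-evaluable for PK. What SAP 12.3.5 mainly adds is the option to drop a reportable, in-window value on its appearance.

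**Step 2: effect of one exclusion, without any distribution.** Let r be the dropped value divided by the mean of all n values. Then

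relative fall in the mean = (r − 1)/(n − 1).

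With n = 24:

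- Dropping a value of 0 gives (0 − 1)/23 = −4.3%, a rise of 4.3%. Concentrations cannot be negative, so this is the largest upward shift one exclusion can cause.
- Dropping a value 3.53 times the mean gives 2.53/23 = 11.0%, a fall of 11.0%.

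The rule is neutral in wording but not in effect: the upward shift is capped at 4.3% and the downward shift has no comparable cap.

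**Step 3: how large r is likely to be.** Assumption: lognormal troughs at one visit with CV between 50% and 200%, so σ = √ln(1 + CV²). For each setting 100,000 samples were simulated and the highest one or two values removed. Median relative falls at n = 24:

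| CV | σ | Mean, top 1 dropped | SD, top 1 dropped* | Maximum, top 1 dropped* | Mean, top 2 dropped |
|---|---|---|---|---|---|
| 50% | 0.472 | 5.2% | 14.4% | 14.6% | 9.4% |
| 100% | 0.833 | 11.0% | 21.4% | 24.3% | 18.9% |
| 150% | 1.086 | 15.7% | 26.2% | 30.4% | 26.4% |
| 200% | 1.269 | 19.4% | 29.9% | 34.7% | 32.0% |

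*Applies only if the value is also left out of these statistics, which SAP 12.3.5 does not say.

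Check against Step 2: 5.2% implies r = 1 + 23 × 0.052 = 2.2, and 19.4% implies r = 1 + 23 × 0.194 = 5.5.

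**Step 4: fewer subjects, or many values below quantification.** With 18 subjects (assumed attrition), dropping the highest value lowers the mean by 6.3% to 22.2% over the same CV range; with 12 subjects, by 8.2% to 26.2%. If half the values are assumed to be below quantification and set to 0, the fall at n = 24 is 15.5% (CV 100%) to 22.9% (CV 200%), and at n = 12 it is 24.2% to 32.6%.

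**The case against.** The case for leaving the text alone has real substance.

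- **Nothing is hidden.** A reader might infer that high values vanish. They do not: laboratory values are listed as reported, exclusions are flagged, and reasons are given. Appendix B plans individual listings for both analytes by week. With at most 24 subjects and three time points, anyone holding the listings can rebuild the full summary. This stands. It does not repair the summary table and mean plot, which are what most readers will use.
- **Scope.** A reader might infer that the SD, CV and maximum certainly shrink too. SAP 12.3.5 speaks only of mean concentrations, and Appendix B merely names the statistics in a table title. The overlaid individual plots are likewise not addressed. This stands, so the figures for SD and maximum are conditional.
- **Direction.** A reader might infer that the rule is aimed at high values. It is not; low ones could go as well. This stands as a reading of the text, but values below quantification are already handled by rule, and Step 2 shows that the two directions are not equal in size.
- **Safety.** A reader might infer that the safety conclusions are compromised. The documents class Ctrough as a pharmacokinetic endpoint, separate from the primary safety endpoints; adverse events, local tolerability, ECGs, laboratory tests and vital signs are untouched by this rule.
- **Inference.** The study is single-arm and descriptive, with no test or exposure threshold, so neither type I error nor power is affected. This stands and limits the seriousness.

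The simulation shows the effect of an exclusion if one is made. It says nothing about how likely one is.

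**Conclusion.** The point holds as a weakness in how a primary pharmacokinetic endpoint is summarised. A reportable trough can be removed from the mean on one analyst's impression of the value, and the plan requires no summary that retains it. The likely bias is downward.

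At the cap of 24 subjects, one exclusion of the highest value lowers the mean by a median of 5% to 19%, and by 11% at CV 100%. If the other statistics omit it as well, the SD falls by 14% to 30% and the maximum by 15% to 35%. These sizes rest on an assumed lognormal shape and an assumed CV range, since the documents supply neither. The textual finding does not depend on them.

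The documents do not support reading this as loss of data, as a certain effect on the SD, CV or maximum, or as a flaw in the safety endpoints. It is worth correcting before database lock because the correction is cheap and removes an avoidable source of bias.

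**What to change.** Revise SAP 12.3.5 as follows:

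1. Remove abnormal or implausible appearance as a ground for exclusion.
2. Limit exclusion to causes documented by the site or laboratory: assay failure, sample mix-up or contamination, or a dosing or sampling-time error that means the sample is not a trough within the SAP 12.3.6 window. Because that window has no upper limit other than the next dose, state explicitly how a sample taken after a missed application is classified, so that it is clear which table holds it.
3. Require the decision, with its evidence, before any PK summary is produced.
4. Base the main table and figures on all other reportable values, for every statistic shown. This also settles whether the SD, CV, median, maximum and plots follow the same rule as the mean.
5. Show any summary without further suspected outliers only as a sensitivity table beside the main one.

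Keep the existing flagging and documentation of reasons. The cost is a few sentences, one extra table and possibly a larger CV in the main table. A suspected but undocumented outlier can still be examined in the sensitivity table.

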### **12.3.6 Handling of Actual vs. Planned PK Sampling Timepoints**

Actual post-dose time will be used in the Tables and Listings of individual  $C_{trough}$  values. The PK sample collection window ( $\geq 12$  hrs from previous dose and prior to next dose) will be used to summarize descriptive statistics for  $C_{trough}$  values.

### **12.3.7 Handling of Individual PK Data and Summary Data Formats**

The actual values as provided from the bioanalytical laboratory will be displayed as individual concentration-time listings. Drug concentrations will be used to calculate the mean using descriptive analysis. For summary tables, the descriptive statistics will be rounded to one more digit than the individual values for the arithmetic mean, SD, median and geometric mean, and to the same number of digits for the minimum and maximum values. The number of non-missing observations (N) will be reported as an integer number. The coefficient of variation (CV) (%) and geometric CV% will be reported as a percentage (CV\*100) as an integer number.

## **12.4 Derived and Transformed Data**

### **Baseline**

The Baseline (Day 1, pre-dose) measurement of a variable is the latest non-missing measurement before the first dose of study drug in Study BBI-4000-CL-105

### **Age**

Age (in completed years) will be calculated for each subject as:

$$\text{Age (years)} = (\text{Date of Screening visit} - \text{Date of Birth} + 1) / 365.25$$

## **12.5 Assessment Days and Windows**

The listings will include all assessments. The following assessment windows are established:

- Visit 1: Screening/Enrollment (Week 0 [Day 1])
- Visit 2: Week 4 (Day 28 [ $\pm 3$  days])
- Visit 3: Week 8 (Day 56 [ $\pm 5$  days])
- Visit 4: Week 12 (Day 84 [ $\pm 5$  days])
- Visit 5: Week 16 (Day 112 [ $\pm 5$  days])
- Visit 6: Week 20 (Day 140 [ $\pm 5$  days])
- EOT/Early Termination Visit 7: Week 24 (Day 168 [ $\pm 5$  days])
- End of Study (EOS) Visit 8: Week 26 (Day 182 [ $\pm 5$  days])

## 12.6 Missing Safety and Efficacy Data

Adverse events recorded with ambiguous or missing start dates and times will be assumed to have started after the first dose of study drug on Day 1 of Study BBI-4000-CL-105. Consequently, such AEs will be included in all summaries of treatment-emergent adverse events (TEAE). Start and end dates and times for AEs will be listed as collected.

Where the start or end date of a concomitant medication is ambiguous or missing, the medication will be assumed to have been started before and continued after the first dose of study drug in Study BBI-4000-CL-105. That is, the medication will be listed as both prior and concomitant and included in the summary table of concomitant medications.

All other cases of missing or invalid data will be treated as missing and will not be imputed. Start and end dates for concomitant medications will be listed as collected.

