6.3.3 Medication History

Medications taken within the last month (30 days) prior to first dose of sofrironium bromide gel, 15% under Study BBI-4000-CL-105 and within 1 week prior to Screening/Enrollment (Week 0 [Day 1]) will be recorded in the source document and on the eCRF. Also refer to [Section 6.13](#) concomitant medications and restrictions for additional information.

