6.13.2 Concomitant Medication Restrictions

The following medications will not be permitted during the study period:

- Botulinum toxin to the axillary area
- Newly prescribed anti-anxiety, anti-depressant, and/or psychostimulants (e.g., amphetamine) or drugs with known anticholinergic side effects
- Any cholinergic drug (e.g., bethanechol)
- Newly prescribed serotonergic agonist (or drugs that increase serotonin activity including SSRIs), betablocker, alpha-adrenergic agonist (clonidine), dopamine partial agonist or tricyclic antidepressant treatment
- Anticholinergic agents used to treat conditions such as, but not limited to, hyperhidrosis, asthma, incontinence, gastrointestinal cramps, and muscular spasms by any route of administration (e.g., intravenous, oral, inhaled, topical, etc.)
- Any topical prescription treatment for hyperhidrosis
- Any oral or topical homeopathic or herbal treatment (i.e., alternative therapies such as sage tablets, chamomile, valerian root and St. John's Wort)
- Use of potent inhibitors of cytochrome P450 CYP3A (including grapefruit juice) & CYP2D6 and transporter inhibitor (OCT2/MATE1/MATE2). Use of topical antifungal medications is permitted if not applied in the treatment area.

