# 13 STATISTICAL ANALYSIS

## 13.1 Baseline Parameters, Demographics, Medical History, Hyperhidrosis History, Concomitant Medications, Disposition and Drug/Alcohol Screening, and Pregnancy Testing

- The total number of subjects enrolled in the study.
- Subject demographics and baseline characteristics will include, date of birth, gender, race, ethnicity, height and weight, and age at onset and duration of hyperhidrosis, will be summarized and listed. Descriptive statistics (mean, SD, median, minimum, and maximum for numerical variables; count and percentage for categorical variables) will be presented where applicable.

- Subject medical, hyperhidrosis and medication history will be listed by MedDRA system organ class and preferred term (PT). A listing sorted by subject number, MedDRA system organ class and PT, and onset date will also be presented.
- Subject medication history will be mapped according to the WHODD.
- A listing of subject disposition will include start date and time of first study drug application in the extension study.
- The number of subjects who complete treatment (Day 168 [ $\pm 5$  days], EOT) will be summarized and listed.
- The number of subjects who complete study (Day 182 [ $\pm 5$  days], EOS) will be summarized and listed.
- The number of subjects who prematurely discontinue from the study and reason for discontinuation will be summarized and listed. The number of subjects who prematurely withdraw from study drug but remaining in the study will be summarized.
- Concomitant medications (start date on or after Day 1 of Study BBI-4000-CL-105) will be summarized using descriptive statistics.
- Use of concomitant medications (chronic medications or as needed medications e.g., acetaminophen, EMLA cream) are permitted during the screening and active study period (Day 1 through Day 168 [ $\pm 5$  days]) and will be recorded on the eCRF.
- Changes in concomitant medication usage will be recorded on the eCRF. If the reason for change is related to an AE, the event will be recorded in as an AE in the eCRF.
- Concomitant medications will be mapped according to the WHODD and will be presented in data listings.
- Drug and alcohol screen by visit will be listed.
- Pregnancy test (positive or negative) by visit will be listed.

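### SAP 12.6 classes any medication with one missing or ambiguous date as both prior and concomitant, even when the recorded date rules one of these out

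*SAP*

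**What the plan says.** SAP 12.6 (Missing Safety and Efficacy Data) gives one rule for incomplete medication dates: "Where the start or end date of a concomitant medication is ambiguous or missing, the medication will be assumed to have been started before". The same sentence makes a second assumption about the other end of the record, that use went on past the first CL-105 dose. The sentence after it states the result: "the medication will be listed as both prior and concomitant and included in the summary table of concomitant medications". The same section later adds: "Start and end dates for concomitant medications will be listed as collected".

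SAP 13.1 defines the group to be tabulated by start date alone: "Concomitant medications (start date on or after Day 1 of Study BBI-4000-CL-105) will be summarized using descriptive statistics". It applies no test to the stop date.

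Protocol 6.3.3 brings pre-treatment drugs into the database. It records "Medications taken within the last month (30 days) prior to first dose of sofrironium bromide gel, 15% under Study BBI-4000-CL-105", as well as those taken in the week before the extension's enrolment visit.

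Two planned outputs in SAP Appendix A use the classification: Table 14.1.4 (concomitant medications, Safety Population) and Listing 16.2.4.3 (prior and concomitant medications).

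**The concern.** A missing-date rule should fill the gap and leave the rest of the record alone. This one is triggered by a gap in either date but then makes an assumption about both, so it can replace a fact on the eCRF with its opposite.

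Two outputs are exposed. The first is the count in Table 14.1.4, which could include a drug that was finished before the first application of gel. The second is the prior label in Listing 16.2.4.3, which could be attached to a drug with a documented on-study start. In the second case 12.6 also conflicts with 13.1, under which that drug is plainly concomitant.

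**Working it through.** The plan gives no figure to reproduce. The check applies the 12.6 rule as written to each pattern with at least one date missing, and compares the result with a rule that imputes only the missing date. Days are counted from the first CL-105 dose and are illustrative.

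| Start | Stop | SAP 12.6 as written | Recorded date kept | Conflict with the record? |
|---|---|---|---|---|
| missing | day −10 | prior + concomitant | prior only | yes (case 1) |
| missing | day +30 | prior + concomitant | prior + concomitant | no |
| day −20 | missing | prior + concomitant | prior + concomitant | no |
| day +40 | missing | prior + concomitant | concomitant only | yes (case 2) |
| missing | missing | prior + concomitant | prior + concomitant | no |

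The rule gives the same answer in all five rows and contradicts a recorded date in two.

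**Case 1.** Such records can exist, because Protocol 6.3.3 collects drugs from the 30 days before the first dose. Table 14.1.4 is on the Safety Population, and enrolment is up to 24 (SAP 11). One misclassified subject moves a line by 1/N:

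- N = 24, the maximum: 1/24 = 4.2 percentage points.
- N = 12, assumed for illustration: 1/12 = 8.3 percentage points.

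The shift is zero if the subject already counts on that line through another record.

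**Case 2.** The drug is concomitant under both 12.6 and 13.1, so its Table 14.1.4 entry is correct. Only the added prior label is wrong. The SAP's table list has no prior-medication table, so the label appears only in Listing 16.2.4.3.

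**A related mismatch with 13.1.** Take a drug with complete dates, start day −20 and stop day +30. The start-date definition in 13.1 leaves it out of the concomitant summary, although it was used on treatment. Delete its stop date and 12.6 puts it in. Whether the same drug is tabulated then depends on whether the record is complete. The two sections need to be aligned whatever is decided on cases 1 and 2.

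**The case against.** **The rule is deliberately inclusive.** It parallels the adverse event rule in the same section and never drops an incompletely dated on-treatment drug from the table. That is a reasonable default when the dates leave the question open, and the fix keeps it there. It does not justify overriding a date that settles the question.

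**Case 1 may lie outside the rule.** The sentence concerns concomitant medications, and a drug stopped before the first dose cannot have started on or after Day 1. This is arguable, but it does not dispose of the point. With the start missing, the 13.1 test cannot be applied directly, and the SAP has no stop-date test to remove the record. The rule also assigns prior status, so it is evidently meant to sort prior from concomitant. If it covered only drugs that started on or after Day 1, assuming an earlier start would always be wrong.

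**A reader might infer that the prior label hides violations or confounders of adverse events**, since Protocol 6.13.2 prohibits some classes only when new, for example: "Newly prescribed anti-anxiety, anti-depressant, and/or psychostimulants (e.g., amphetamine) or drugs with known anticholinergic side effects". The documents do not support this. SAP 12.8 has a sponsor designee adjudicate violations from eCRF data, not from a derived label. Dates are listed as collected, so an on-study start stays visible. Protocol 6.13.1 has medication changes recorded, and where an adverse event is the reason, that event recorded too. In case 2 the drug is labelled both, not prior only.

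**A reader might infer that every on-study drug with a blank end date at Week 26 is mislabelled.** That requires an ongoing drug to count as having a missing end date. Neither document says so.

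**Few records may be affected.** Protocol 12.2.4 sends missing data back to sites as queries, and SAP 12.3.1 replaces sparse tables with listings. Both stand as limits on the size of the effect.

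**Conclusion.** The point holds as a minor error in a stated rule. SAP 12.6 contradicts a recorded date in two of the five missing-date patterns. Case 1 can add a subject to a Table 14.1.4 line, worth at least 4.2 percentage points at up to 24 subjects if that subject has no other qualifying record. Case 2 puts a wrong label in one listing and changes no listed table. Case 2 is the firmer of the two, because it conflicts directly with the 13.1 definition; case 1 depends on reading 12.6 as covering drugs whose start is unknown.

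No primary safety or PK endpoint uses the classification. The documents give no rate of incomplete dates. With complete dates, and ongoing drugs not treated as missing an end date, neither case arises.

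**What to change.** Replace both sentences of the medication paragraph in SAP 12.6, the assumption and the explanation that follows it. Changing only the first would leave the second still requiring both labels. Suggested text:

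> If a medication's start or end date is missing or ambiguous, only the missing part is imputed, and recorded date information is not overridden. If the recorded end date is before the first CL-105 dose, the medication is prior only. If the recorded start date is on or after the first CL-105 dose, it is concomitant only. Otherwise it is shown as both and counted in the concomitant medication table. A medication marked ongoing is not treated as having a missing end date.

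Align the SAP 13.1 definition at the same time, so that a drug started before the first dose and still in use afterwards is treated consistently in the two sections. This must go with the ongoing sentence. Otherwise an ongoing drug with a known pre-dose start would fall back on the start-date definition and drop out of Table 14.1.4.

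The cost is two sentences in 12.6, one definition in 13.1, a small programming change, and confirmation of how the eCRF records ongoing use. Aligning 13.1 may bring some completely dated, continuing drugs into Table 14.1.4, so it should be settled before database lock. The line keeping collected dates in the listing stays.
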